10.7. Appendix 7: Premature Withdrawals & Handling of Missing Data

10.7.1. Premature Withdrawals

Element	Reporting Detail
General	• Subject study completion is defined as attendance at Visit 7.
	 Withdrawn subjects were not replaced in the study.
	 All available data from subjects who were withdrawn from the study will be listed and all available planned data will be included in summary tables and figures, unless otherwise specified.

10.7.2. Handling of Missing Data

Element	Reporting Detail
General	 Missing data occurs when any requested data is not provided, leading to blank fields on the collection instrument : These data will be indicated by the use of a "blank" in subject listing displays unless all data for a specific visit are missing in which case the visit is not displayed in the listing. Answers such as "Not applicable" and "Not evaluable" are not considered to be missing data and should be displayed as such. No imputation will be made for any missing numerical data, except in the sensitivity analysis of primary endpoints to assess the impact of missing data on study results. Missing data will generally not be considered in the calculation of percentages (i.e., the denominator will not include subjects who have missing data at a given time point).

Responder	•	Subjects with a missing baseline will have responder status as missing. Subjects with missing post-baseline data and a subsequent non-missing scheduled assessment will not be considered a responder or non-responder but will be left as missing.
	•	Subjects with a missing post-baseline assessment with no subsequent non- missing assessments will be considered a non-responder for that and all subsequent time points.
	•	Subjects with a baseline but all missing post-baseline data will be considered a non-responder at all time points.

10.7.2.1. Handling of Missing Dates

Element	Reporting Detail
General	Partial dates will be displayed as captured in subject listing displays.

Element	Reporting Detail
Adverse Events	 The eCRF allows for the possibility of partial dates (i.e., only month and year) to be recorded for AE start and end dates; that is, the day of the month may be missing. In such a case, the following conventions will be applied for calculating the time to onset and the duration of the event: Missing Start Day: First of the month will be used unless this is before the period start date of study treatment; in this case the study treatment period start date will be used and hence the event is considered On-treatment as per Appendix 4: Treatment States. Missing Stop Day: Last day of the month will be used, unless this is after the period stop date of study treatment; in this case the study treatment period stop date of study treatment; in this case the study treatment period stop date of study treatment; in this case the study treatment period stop date of study treatment; in this case the study treatment period stop date will be used.

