10.4.1.2. Treatment States for AE Data

Classification of an AE as pre-, on- or post-treatment will be made with reference to the study treatment start and stop dates for each period and the AE onset date. If the AE onset date is missing or partial then the AE will be considered on-treatment unless there is evidence to the contrary (e.g. the month of the onset date is present and is less than the month of the first dose of study treatment). AEs with onset on the day after the last day of treatment will be considered on-treatment. Other AEs with onset during the wash-out or follow-up periods, or following IP discontinuation will be considered post-treatment but will be assigned to the treatment received in the previous period. AEs with missing or partial onset dates which are not classified will be included in listings only. AEs reported by subjects who did not receive treatment will be considered pre-treatment.

Treatment State	Definition
Pre-Treatment	AE Onset Date < First Study Treatment Start Date
On-Treatment	If AE onset date is on or after treatment start date & on or before treatment stop date. Study Treatment Start Date \leq AE Start Date \leq Study Treatment Stop Date + 1 day
Post-Treatment	If AE onset date is after the treatment stop date plus 1 day.
	AE Start Date > Study Treatment Stop Date + 1 day
Onset Time	If Treatment Start Date > AE Onset Date: = AE Onset Date - Treatment Start Date
Since 1 st Dose	If Treatment Start Date ≤ AE Onset Date: = AE Onset Date - Treatment Start Date +1
(Days)	Missing otherwise.
Duration (Days)	AE Resolution Date – AE Onset Date + 1
Drug-related	If relationship is marked 'YES' on [Inform/CRF OR value is missing].

NOTES:

If the study treatment stop date is missing then the AE will be considered to be On-Treatment.

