10.7.2.2. Handling of Partial Dates

Element	Reporting Detail
Concomitant Medications	 Partial dates for any concomitant medications recorded in the CRF will be imputed using the following convention: If the partial date is a start date, a '01' will be used for the day and 'Jan' will be used for the month If the partial date is a stop date, a '28/29/30/31' will be used for the day (dependent on the month and year) and 'Dec' will be used for the month. The recorded partial date will be displayed in listings.
Adverse Events	 Any partial dates for adverse events will be raised to data management. If the full date cannot be ascertained, the following assumptions will be made: If the partial date is a start date, a '01' will be used for the day and 'Jan' will be used for the month. However, if these results in a date prior to Week 1 Day 1 of the respective period and the event could possibly have occurred during treatment from the partial information, then the pWeek 1 Day 1 date for the respective period will be assumed to be the start date. The AE will then be considered to start on-treatment (worst case). If the partial date is a stop date, a '28/29/30/31' will be used for the month unless this is after the period stop date of study treatment; in this case the period study treatment stop date will be used.

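### The partial-date rules for adverse events cap the stop date at the last dose, giving stop dates before onset, and leave open which crossover period a month-only onset belongs to

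*SAP*

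**What the plan says.** SAP 10.7.2.1 gives conventions for an AE date with the day missing and states their purpose: "the following conventions will be applied for calculating the time to onset and the duration of the event".

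- **Stop day missing (10.7.2.1):** "Missing Stop Day: Last day of the month will be used, unless this is after the period stop date of study treatment", in which case the treatment stop date of the period replaces it. The AE row of 10.7.2.2 carries the same limit: "unless this is after the period stop date of study treatment; in this case the period study treatment stop date will be used".
- **Onset day missing (10.7.2.1):** "First of the month will be used unless this is before the period start date of study treatment"; if it is before, "the study treatment period start date will be used and hence the event is considered On-treatment as per Appendix 4: Treatment States".
- **Onset partial (10.7.2.2):** the first of the month, or of January if the month is unknown. This moves to Day 1 of the respective period only if "the event could possibly have occurred during treatment from the partial information". The result is labelled the worst case.
- **Treatment state (10.4.1.2):** "If the AE onset date is missing or partial then the AE will be considered on-treatment unless there is evidence to the contrary". Onset up to one day after the treatment stop date is on-treatment. Later washout and follow-up events "will be considered post-treatment but will be assigned to the treatment received in the previous period". Duration is resolution date minus onset date plus 1.

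Protocol 4.1 collects AEs from Day 1 to the follow-up contact, so AEs after the last dose of each period are expected.

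**The concern.** Neither date rule requires the imputed stop to fall on or after the onset. The cap is a last-dose date, and a post-treatment AE by definition starts after it. The rule would then return impossible durations for that class of event, and it would shorten an on-treatment AE that runs on past the last dose.

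The onset side matters because, in a crossover, the period in which an AE is placed decides which drug it counts against. The SAP plans separate on-treatment and post-treatment AE tables by treatment (Appendix 13, safety tables). If the reference period is not named, one event can appear under either drug. The worst-case label does not settle this, because moving an event to the second drug removes it from the first.

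**Working it through.** **Inputs.** 8-week periods, and a washout of 21 ± 3 days between Visit 4 and Visit 5 (Protocol 4.2 and 7.1). No study drug is given at Visits 4 and 7 (Protocol 7.3.1), so the last dose is taken as the day before. Duration formula and state windows are from SAP 10.4.1.2. The plan states no figure of its own to reproduce.

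**1. Stop-date cap, general case.** Let P be the period's treatment stop date. A post-treatment AE has onset at P + 2 or later, and its resolution month ends on or after onset. Month end is therefore always after P, the cap always applies, and the imputed stop is P. Duration is at most P − (P + 2) + 1 = −1 day. For onset on P + 1, which is classed as on-treatment, it is P − (P + 1) + 1 = 0.

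**2. Worked schedule.** Period 1 dosing 8 Aug to 1 Oct 2016; Visit 4 on 2 Oct; Period 2 dosing 23 Oct to 16 Dec.

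| Event | Stop recorded | Imputed stop | Duration under rule |
|---|---|---|---|
| Washout, onset 9 Oct | Oct | 1 Oct | 1 − 9 + 1 = −7 (month end: 31 − 9 + 1 = 23) |
| Follow-up, onset 20 Dec | Dec | 16 Dec | 16 − 20 + 1 = −3 |
| Day after last dose, onset 2 Oct | Oct | 1 Oct | 1 − 2 + 1 = 0 |
| On-treatment, onset 25 Sep | Oct | 1 Oct | 6 + 1 = 7 (month end: 36 + 1 = 37) |

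The washout row uses the Period 1 cap because 10.4.1.2 ties washout AEs to the previous period. Using the Period 2 stop date would avoid the negative value. The follow-up row has no later period to turn to.

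**3. Onset recorded only as October, same schedule.** Read against Period 1, the first of the month (1 Oct) is not before 8 Aug, so it stands, and it is the last dose day: on-treatment, drug 1. Read against Period 2, 1 Oct is before 23 Oct, so the onset becomes 23 Oct: on-treatment, drug 2. If the true onset was 9 Oct, the correct state is post-treatment, drug 1, and neither reading gives it.

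**4. How often one month holds both doses.** The last Period 1 dose and first Period 2 dose are k = washout + 1 days apart. In a month of L days, L − k dates keep both inside it. Over a year the share is (365.25 − 12k)/365.25:

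- 18-day washout, k = 19: (365.25 − 228)/365.25 = 37.6%
- 21-day washout, k = 22: (365.25 − 264)/365.25 = 27.7%
- 24-day washout, k = 25: (365.25 − 300)/365.25 = 17.9%

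**5. Wider ambiguity.** A month-only onset truly in the washout can be read to either drug whenever its month also contains Visit 5. Assume onset is equally likely on each washout day from P + 2 (20 days for a 21-day washout, on average 10.5 days before Visit 5). The share is 1 − 12 × 10.5/365 = 65%. The same formula gives 1 − 12 × 9/365 = 70% at 18 days and 1 − 12 × 12/365 = 61% at 24 days. At 21 days this divides into 31% that are on-treatment under both readings and 34.5% that are post-treatment on drug 1 or on-treatment on drug 2. The other 34.5% can only be drug 1.

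**6. The two onset rules side by side.** 10.7.2.2 moves an onset to Day 1 only if on-treatment onset is possible. 10.7.2.1 has no such condition. Read literally, it moves an onset recorded only as July to 8 Aug in the schedule above and calls it on-treatment. That contradicts 10.4.1.2, whose own example of contrary evidence is an onset month earlier than the month of first dose. The SAP also plans pre-treatment SAE tables, so such events are foreseen.

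**The case against.** The strongest reply is that the SAP already limits the damage. Partial AE dates go to data management first and are imputed only if the full date cannot be found. Listings show partial dates as captured. SAP 10.4.1.2 yields to contrary evidence, which a report at Visit 4, Visit 5 or during washout could supply, and it sends unclassified partial-onset events to listings only. AE state depends on onset, not stop date, and no planned safety table summarises AE duration; the exacerbation duration summary has its own formula. All of this stands and limits the size of the point. It does not supply a check that stop follows onset, and it does not name the reference period.

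A reader might infer more than the documents support:

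- **That the rules ignore the crossover.** They refer to period start and stop dates, and 10.4.1.2 handles the washout explicitly. The gap is in how the period is chosen.
- **That every month-only onset is forced on-treatment.** If the first of the month falls in the washout more than one day after the last dose, the Period 1 reading leaves the event post-treatment on drug 1.
- **That attribution is wholly at the programmer's discretion.** The contrary-evidence and listings-only clauses constrain it.
- **That AE listings will print negative durations.** The listing shells are not in the documents, so this cannot be shown.
- **That the safety comparison is tilted towards one drug.** Sequences are allocated equally (Protocol 6.3), so a consistent choice of Period 1 or Period 2 would move events towards both drugs.

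**Conclusion.** The point holds as a minor drafting defect with two parts. First, the stop-date cap gives a stop before onset for every follow-up AE with a month-only stop, and for every such washout AE under the previous-period attribution of 10.4.1.2. It also truncates on-treatment AEs that continue past the last dose. Second, the reference period for a partial onset is undefined, and 10.7.2.1 and 10.7.2.2 differ on when an onset may be moved.

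The reach is limited to AEs whose dates stay partial after query. For those it touches derived duration, time to onset, and on-treatment and post-treatment counts by drug. The 28% (18% to 38%) is a share of calendar dates for Visit 4, and the 65% a share of washout days under uniform onset. Neither is an expected number of events, because the documents give no partial-date rate. The primary analysis is unaffected.

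**What to change.** Merge the two AE date rules into one, settled before the randomization codes are released:

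1. **Stop date.** Remove the treatment-stop cap. Use month end, limited only by death or last study contact, and require the imputed stop to be no earlier than onset.
2. **Keep what 10.7.2.2 adds.** Simply deleting its AE row would lose the data-management query, the condition that on-treatment onset be possible, and the rule for a missing month. Carry all three into the merged rule.
3. **Name the reference period.** Use the visit at which the AE was reported, where available, as contrary evidence under 10.4.1.2. For example, an AE already reported before the Visit 5 dose cannot belong to Period 2. Otherwise apply a stated convention and flag the event.

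The cost is SAP wording and minor programming. The documents do not show whether the eCRF stores the visit of first report, which is why the fallback convention is needed.

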10.7.2.2. Handling of Partial Dates

Element	Reporting Detail
Concomitant Medications	 Partial dates for any concomitant medications recorded in the CRF will be imputed using the following convention: If the partial date is a start date, a '01' will be used for the day and 'Jan' will be used for the month If the partial date is a stop date, a '28/29/30/31' will be used for the day (dependent on the month and year) and 'Dec' will be used for the month. The recorded partial date will be displayed in listings.
Adverse Events	 Any partial dates for adverse events will be raised to data management. If the full date cannot be ascertained, the following assumptions will be made: If the partial date is a start date, a '01' will be used for the day and 'Jan' will be used for the month. However, if these results in a date prior to Week 1 Day 1 of the respective period and the event could possibly have occurred during treatment from the partial information, then the pWeek 1 Day 1 date for the respective period will be assumed to be the start date. The AE will then be considered to start on-treatment (worst case). If the partial date is a stop date, a '28/29/30/31' will be used for the month unless this is after the period stop date of study treatment; in this case the period study treatment stop date will be used.

10.7.2.3. Handling of Missing Data for Statistical Analysis

For analysis of trough FEV1 at Week 8, sensitivity analyses will be produced using tipping point methodology (Ratitch, 2013). These methods are detailed in Section 7.1.2.

10.8. Appendix 8: Multicenter Studies

10.8.1. Methods for Handling Centres

- This study will be randomized centrally.
- Results will be presented for all centres combined; centre will not be accounted for in statistical analyses.

10.9. Appendix 9: Examination of Covariates, Subgroups & Other Strata

10.9.1. Handling of Covariates

- Consistency of treatment effect across covariates fitted in the primary efficacy endpoint analysis models will be examined by fitting separate models to examine treatment by period baseline, treatment by mean baseline and treatment by period interactions.
- No formal statistical analysis of sub-groups of the study population will be performed.
- The interaction terms will be tested at the 10% significance level. Significant interactions (<0.10) will be investigated further, for example running the analysis by each category. Continuous covariates may be grouped into dichotomous categories (values above and below median).

10.10. Appendix 10: Multiple Comparisons & Multiplicity

10.10.1. Handling of Multiple Comparisons & Multiplicity

See Section 2.4 for details on inferences that can be drawn on primary and 'other' endpoints for non-inferiority and superiority.

10.11. Appendix 11: Model Checking and Diagnostics for Statistical Analyses

Distributional assumptions underlying the model used for analyses using MMRM (non binary data) will be examined by obtaining a normal probability plot of the residuals and a plot of the residuals versus the fitted values (i.e. checking the normality assumption and constant variance assumption of the model respectively) to gain confidence that the model assumptions are reasonable.

10.12. Appendix 12 – Abbreviations & Trade Marks

10.12.1. Abbreviations

Abbreviation	Description			
AE	Adverse Event			
A&R	Analysis and Reporting			
ASE	All Subjects Enrolled			
ATC	Anatomical-Therapeutic-Chemical			
САТ	COPD Assessment Test			
CI	Confidence Interval			
CS	Clinical Statistics			
CSR	Clinical Study Report			
CTR	Clinical Trial Register			
DOB	Date of Birth			
DP	Decimal Places			
DPI	Dry Powder Inhaler			
eCRF	Electronic Case Record Form			
E-RS	EXACT Respiratory Symptoms			
FEV ₁	Forced Expiratory Volume in One Second			
FVC	Forced Vital Capacity			
GOLD	Global Initiative for Chronic Obstructive Lung Disease			
IC	Inspiratory Capacity			
ICH	International Conference on Harmonisation			
ICS	Inhaled Corticosteroid			
IDSL	Integrated Data Standards Library			
IMMS	International Modules Management System			
IP	Investigational Product			
ITT	Intent-To-Treat			
GUI	Guidance			
KR	Kenwood Roger			
LS	Least squares			
mMRC	Modified Medical Research Council			
MMRM	Mixed Model Repeated Measures			
PD	Protocol Deviation			
PDMP	Protocol Deviation Management Plan			
PP	Per Protocol			
QC	Quality Control			
RAP	Reporting & Analysis Plan			
RAMOS	Randomization & Medication Ordering System			
SAC	Statistical Analysis Complete			
SAE	Serious Adverse Event			
SE	Standard Error			
SOP	Standard Operation Procedure			
ТА	Therapeutic Area			

Abbreviation	Description
TFL	Tables, Figures & Listings
GSK	GlaxoSmithKline
UMEC	Umeclidinium Bromide
VI	Vilanterol

10.12.2. Trademarks

Trademarks of the GlaxoSmithKline Group of Companies

ELLIPTA

Trademarks not owned by the GlaxoSmithKline Group of Companies

SAS

10.13. Appendix 13: List of Data Displays

10.13.1. Data Display Numbering

The following numbering will be applied for RAP generated displays:

Section	Tables	Figures
Study Population	1.1 to 1.40	
Efficacy	2.1 to 2.48	2.1 to 2.13
Safety	3.1 to 3.23	
Section	Listings	
ICH Listings	1 to 17	
Other Listings	18 to 32	

10.13.2. Mock Example Shell Referencing

Non IDSL specifications will be referenced as indicated and if required example mock-up displays provided in a separate document.

Section	Figure Table		Listing	
Study Population	SP_Fn	SP_Tn	SP_Ln	
Efficacy	E_Fn	E_Tn	E_Ln	
Safety	S_Fn	S_Tn	S_Ln	

NOTES:

• Non-Standard displays are indicated in the 'IDSL / TST ID / Example Shell' or 'Programming Notes' column using the reference convention detailed in this table.

10.13.3. Deliverable [Priority]

Delivery	Description
SAC	Final Statistical Analysis Complete

10.13.4. Study Population Tables

Study Population Tables						
No.	Population	IDSL / TST ID / Example Shell	Title	Programming Notes	Deliver-able	
Subject Dispo	osition	·		•		
1.1.	ASE		Summary of Subject Populations and Reasons for Screen Failures		SAC	
1.2.	ITT		Summary of Attendance at Each Clinic Visit		SAC	
1.3.	ITT		Summary of Completion and Premature Discontinuation of Study Treatment		SAC	
1.4.	ITT		Summary of Study Completion and Withdrawal		SAC	
1.5.	ITT		Summary of Subject Discontinuation at Each Period		SAC	
1.6.	ITT		Summary of Subject Withdrawal at Each Period		SAC	
1.7.	ITT		Summary of Reasons for Discontinuation of Treatment at End of Each Period		SAC	
1.8.	ITT		Summary of Reasons for Withdrawal at End of Each Period		SAC	
1.9.	ITT	IDSL – NS3	Summary of Number of Subjects by Country and Centre	Replace 'Centre ID' header with 'Investigator at Centre'	SAC	
Protocol Devi	ations					
1.10.	ASE	IDSL – IE2	Summary of Inclusion/ Exclusion/ Randomization Criteria Deviations for Screen or Run-in failures	Include 'Number of Screen or Run-in Failures' row at the top of the table. This is to be used as the denominator for the % calculations.	SAC	
1.11.	ITT	IDSL – IE1	Summary of Inclusion/ Exclusion/ Randomization Criteria Deviations for Intent-to-treat		SAC	

Study Population Tables						
No.	Population	IDSL / TST ID / Example Shell	Title	Programming Notes	Deliver-able	
1.12.	ITT	SP_T09 (DV1A)	Summary of Important Protocol Deviations		SAC	
1.13.	ITT	SP_T10	Summary of Exclusions from the Per Protocol Analysis		SAC	
Demography						
1.14.	ITT	IDSL - DM1	Summary of Demographic Characteristics, Intent-to-treat		SAC	
1.15.	PP	IDSL - DM1	Summary of Demographic Characteristics, Per Protocol		SAC	
1.16.	ITT	IDSL - DM5	Summary of Race and Racial Combinations		SAC	
1.17.	ITT	IDSL – DM6	Summary of Race and Racial Combination Details		SAC	
1.18.	ASE	EMA Table 1	Summary of Number of Subjects Enrolled by Country	EMA Reporting Package. Macro: EMA_COUNTRY	SAC	
1.19.	ASE	EMA Table 2	Summary of Number of Subjects Enrolled by Age Category	EMA Reporting Package. Macro: EMA_AGEGRP	SAC	
Medical Cond	ition & Concomitant Me	edications				
1.20.	ITT	IDSL – MH4	Summary of Current Medical Conditions		SAC	
1.21.	ITT	IDSL – MH4	Summary of Past Medical Conditions		SAC	
1.22.	ITT	SP_T11	Summary of Family History of Cardiovascular Risk Factors at Screening		SAC	
1.23.	ITT	SP_T12	Summary of COPD History at Screening		SAC	
1.24.	ITT	SP_T13	Summary of COPD Exacerbation History at Screening		SAC	
1.25.	ITT	IDSL-SU1	Summary of Smoking History at Screening	Using Years Smoked, Cigarettes/Day and Smoking Pack Years	SAC	

Study Population Tables						
No.	Population	IDSL / TST ID / Example Shell	Title	Programming Notes	Deliver-able	
1.26.	ITT	SP_T14	Summary of Smoking Status at Screening		SAC	
1.27.	ІТТ	SP_T15	Summary of COPD Concomitant Medications Not Given for a COPD Exacerbation Taken Before Run-in		SAC	
1.28.	ІТТ	SP_T15	Summary of COPD Concomitant Medications Not Given for a COPD Exacerbation Taken During Run-in or Washout	Display treatments instead of total	SAC	
1.29.	ІТТ	SP_T15	Summary of COPD Concomitant Medications Not Given for a COPD Exacerbation Taken On-treatment	Display treatments instead of total	SAC	
1.30.	ІТТ	SP_T15	Summary of COPD Concomitant Medications Not Given for a COPD Exacerbation Taken Post-treatment			
1.31.	ІТТ	SP_T15	Summary of Concomitant Medications Given for a COPD Exacerbation Taken On-treatment	Display treatments instead of total	SAC	
1.32.	ІТТ	SP_T15	Summary of Concomitant Medications Given for a COPD Exacerbation Taken During Washout	Display treatments instead of total		
1.33.	ІТТ	SP_T15	Summary of Concomitant Medications Given for a COPD Exacerbation Taken Post-treatment			
1.34.	ІТТ	IDSL – CM1	Summary of Non-COPD Concomitant Medications Taken On-treatment	Display ATC and ingredient by treatments	SAC	
1.35.	ІТТ	IDSL – CM1	Summary of Non-COPD Concomitant Medications Taken Post-treatment	Display ATC and ingredient by total	SAC	
Baseline Sev	verity					
1.36.	ITT		Summary of Screening Lung Function Test Results		SAC	
1.37.	ITT		Summary of GOLD Grade 1-4, GOLD mMRC Category A- D, GOLD CAT Category A-D and Reversibility at Screening		SAC	
1.38.	ITT		Summary of Screening IC Results		SAC	

Study Population Tables							
No.	No. Population IDSL / TST ID / Example Shell		Title	Programming Notes	Deliver-able		
1.39.	ITT		Summary of mMRC Dyspnoea Scale at Screening		SAC		
Treatment							
1.40.	ITT		Summary of Overall Percentage Treatment Compliance		SAC		

